3. STUDY DESIGN

This is a Phase 1, randomized, observer blind, placebo-controlled, dosage-escalation, single center study, enrolling healthy adults. In total, approximately 288 healthy non-pregnant female and male adults (18 to 45 years of age) will be enrolled in the study in the ratio of 3:1. There is a higher ratio of female to male subjects because the RSV F subunit vaccine is ultimately intended for use in pregnant women. Men are still being included in this study because the vaccine may also be tested in the future in elderly subjects.

Approximately 288 healthy subjects will be enrolled (1:1:1) in a stepwise dosage-escalation manner in to one of three cohorts (cohort 1: low dosage of RSV F subunit vaccine [45 µg], cohort 2: middle dosage of RSV F subunit vaccine [90 µg], and cohort 3: high dosage of RSV F subunit vaccine [135 µg]). Cohort 1 will be enrolled first, followed by cohort 2, and finally cohort 3. Within each cohort subjects will be randomly allocated (1:1:1:1) to receive vaccine with no adjuvant, vaccine with aluminum hydroxide, vaccine with MF59, or saline placebo, as outlined in [Table 4-1](#). All subjects will receive two doses of a 0.5 mL intramuscular injection of the vaccine, with adjuvant (aluminum hydroxide [1 mg] or MF59 [0.25 mL; 9.75 mg squalene and surfactants]), the vaccine without adjuvant, or saline placebo. There will be approximately 24 subjects in each active treatment group and 24 placebo subjects per cohort) ([Table 4-1](#)).

The schedule of time and events, including whether a visit is a telephone call or a clinic visit is displayed in [Table 3-1](#).

Table 3-1: Times and Events Table

Study Period	Screen	Vaccine Dose #1 & Safety Follow-up				Vaccine Dose #2 & Safety Follow-up					Post-vaccination Follow-up				
		Clinic Visit	Clinic Visit	Reminder Call	Clinic Visit	Phone Call	Clinic Visit	Reminder Call	Clinic Visit	Phone Call	Clinic Visit	Clinic Visit	Clinic Visit	Clinic Visit	Clinic Visit
Study Day	-28 to -3	1	3, 5	8	15, 22	29	31, 33	36	43, 50	57	85	113	181	209	271, 366, 394
Days post 1 st dose		0	2, 4	7	14, 21	28	30, 32	35	42, 49	56					
Days post 2 nd dose						0	2, 4	7	14, 21	28	56				
Study Visit Window (min-max) in Days (d)	n/a	n/a	-1/+1	-1/+4 d	-1/+1	+14 d	-1/+1	-3/+3 d	-1/+1	-7/+7 d	-7/+7 d	-7/+7 d	-7/+7 d	-14/+14 d	-7/+7 d
Visit Number	Screening	1		2	3, 4	5		6	7, 8	9	10	11	12	13	14, 15, 16
Informed Consent	X														
Medical History	X														
Physical Exam ^a	X	X ^b		X		X ^b		X		X	X	X	X	X	
Safety Laboratory Blood draw [max: 10 mL whole blood] ^c	X	X ^b		X		X ^b		X		X					
Urinalysis ^d	X	X ^b		X		X ^b		X		X					
Pregnancy Test	X	X ^b				X ^b									
Exclusion/Inclusion Criteria	X														
Randomization		X ^b													
Serology Blood draw [max: 15 mL whole blood] ^e		X ^b				X ^b				X			X		

Study Period	Screen	Vaccine Dose #1 & Safety Follow-up				Vaccine Dose #2 & Safety Follow-up					Post-vaccination Follow-up				
Type of Visit	Clinic Visit	Clinic Visit	Reminder Call	Clinic Visit	Phone Call	Clinic Visit	Reminder Call	Clinic Visit	Phone Call	Clinic Visit	Clinic Visit	Clinic Visit	Clinic Visit	Clinic Visit	Phone Call
Study Day	-28 to -3	1	3, 5	8	15, 22	29	31, 33	36	43, 50	57	85	113	181	209	271, 366, 394
Days post 1 st dose		0	2, 4	7	14, 21	28	30, 32	35	42, 49	56					
Days post 2 nd dose						0	2, 4	7	14, 21	28	56				
Study Visit Window (min-max) in Days (d)	n/a	n/a	-1/+1	-1/+4 d	-1/+1	+14 d	-1/+1	-3/+3 d	-1/+1	-7/+7 d	-7/+7 d	-7/+7 d	-7/+7 d	-14/+14 d	-7/+7 d
Visit Number	Screening	1		2	3, 4	5		6	7, 8	9	10	11	12	13	14, 15, 16
2 ^o Exploratory Obj. Blood Draw [max: 50 mL whole blood] ^f		X ^b		X		X ^b							X		
Study Vaccine Administered ^g		V				V									
30 Minutes Post Injection Assessment (Local/ Systemic AEs, Body Temperature) ^h		X				X									
Local/Systemic AEs, Body Temperature, Other Indicators of Reactogenicity ⁱ		X				X									
Diary Card Training ^j		X				X									
Diary Card Dispensed ^k		X				X									
Diary Card Reminder Call ^l			X				X								

Study Period	Screen	Vaccine Dose #1 & Safety Follow-up				Vaccine Dose #2 & Safety Follow-up					Post-vaccination Follow-up				
Type of Visit	Clinic Visit	Clinic Visit	Reminder Call	Clinic Visit	Phone Call	Clinic Visit	Reminder Call	Clinic Visit	Phone Call	Clinic Visit	Clinic Visit	Clinic Visit	Clinic Visit	Clinic Visit	Phone Call
Study Day	-28 to -3	1	3, 5	8	15, 22	29	31, 33	36	43, 50	57	85	113	181	209	271, 366, 394
Days post 1 st dose		0	2, 4	7	14, 21	28	30, 32	35	42, 49	56					
Days post 2 nd dose						0	2, 4	7	14, 21	28	56				
Study Visit Window (min-max) in Days (d)	n/a	n/a	-1/+1	-1/+4 d	-1/+1	+14 d	-1/+1	-3/+3 d	-1/+1	-7/+7 d	-7/+7 d	-7/+7 d	-7/+7 d	-14/+14 d	-7/+7 d
Visit Number	Screening	1		2	3, 4	5		6	7, 8	9	10	11	12	13	14, 15, 16
Diary Card Reviewed and Collected ^m				X				X							
Telephone Contact for Review of Safety Data ⁿ					X				X						
Assess all AEs, including SAEs and NOCDs Leading or not to Study Withdrawal ^o		X		X		X		X		X	X	X	X	X	X
Assess for AESIs ^p		X		X		X		X		X	X	X	X	X	X
Prior/Concomitant Medications/vaccines ^q	X	X		X		X		X		X	X	X	X	X	
Study Termination ^r															X

- Physical examination must be performed by a qualified health professional in accordance with local regulations and licensing requirements designated within the Site Responsibility Delegation Log. See protocol [section 6.2](#) for components of physical examination by visit.
- Procedure to be performed prior to vaccination.
- Safety laboratory assays that will be included are listed in protocol [section 3.5.3](#).
- Urinalysis testing will include at a minimum protein, glucose, and presence of red blood cells.

- e. Maximal blood draw refers to volume drawn for each type of assay at each specified visit. See protocol [section 3.5.1](#) for greater detail regarding blood sampling volumes.
- f. The first 10 subjects enrolled in each treatment group of Cohort 3 who agree to the additional blood draws will need to sign an additional consent prior to the blood draw for the secondary exploratory objective.
- g. Subjects will receive two doses of vaccine or placebo according to the study randomization scheme.
- h. A 30 minute post-injection local and systemic adverse event and body temperature measurement will be performed by the subject under site staff supervision at the clinic during Visit 1 and Visit 5.
- i. Beginning 6 hours following study vaccine administration at Visit 1 and Visit 5, and daily thereafter through 7 days after each vaccination, solicited local and systemic adverse events including other reactions (i.e. body temperature measurements and use of analgesics/antipyretics) will be reported daily by the subject on a diary card.
- j. Subjects will receive training on the diary card at Visit 1 and Visit 5.
- k. The diary card will be dispensed at Visit 1 and Visit 5, and subjects will be reminded that diary cards must be returned at the next clinic visit (Visit 2 or Visit 6).
- l. Site staff will contact subjects by phone 2 and 4 days after each vaccination to remind them to complete their diary cards each day, and to bring the diary cards to their next clinic visit.
- m. Review of safety data captured on diary cards will be completed at Visit 2 and Visit 6. Diary cards will be collected and stored with subject files.
- n. Safety data will be collected for 28 days following each vaccination. At 14 and 21 days after each dose, subjects will be interviewed by site staff using a scripted interview for collection of safety data. These safety data will be transcribed on source documents by the site staff performing the interviews.
- o. All medically attended AEs that lead to an unscheduled visit to a healthcare practitioner and/or a visit to the emergency department or its equivalent will be collected for 28 days following signing of the informed consent. SAEs, NOCDs and AEs leading to study or vaccine withdrawal will be collected through 1 year after receipt of the second dose. Please see protocol [section 6.6](#) for greater detail regarding methods for SAE and AEs leading to study or vaccine withdrawal collection.
- p. Adverse events of special interest (AESIs) will also be documented in all study subjects for the duration of the study. Monitoring for AESIs will be extended through 1 year after receipt of the second dose and will be accomplished at clinic visits or by a telephone follow-up call. A tabulation of all AESIs, categorized by MedDRA preferred terms and assessed relationship to study vaccine will be submitted as an addendum to the Clinical Study Report (CSR) if not included in the CSR.
- q. Collect concomitant medications and vaccination history according to the study procedures outlined in protocol [section 3.2.5](#) and [5.4](#).
- r. Any subject who terminates the study after receipt of vaccine (prior to Visit 9) is recommended to undergo study-related procedures required at Visit 9. For subjects who terminate after Visit 9, a telephone contact to assess for SAEs/AEs and associated concomitant medications is required.

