4. RANDOMIZATION AND BLINDING

4.1 Method of Group Assignment and Randomization

Subjects will be enrolled in a stepwise dosage-escalation manner into one of three cohorts:

- Cohort 1: low dosage of RSV F subunit vaccine [45 µg],
- Cohort 2: middle dosage of RSV F subunit vaccine [90 µg], and
- Cohort 3: high dosage of RSV F subunit vaccine [135 µg]).

Within each cohort, subjects will be randomly allocated (1:1:1:1) to receive vaccine with no adjuvant, vaccine with aluminum hydroxide, vaccine with MF59, or placebo, as outlined in [Table 4.1](#). All subjects will receive two doses of a 0.5 mL intramuscular injection of the vaccine with adjuvant (aluminum hydroxide [1 mg] or MF59 [0.25 mL; 9.75 mg squalene and surfactants]), the vaccine without adjuvant, or saline placebo. There will be approximately 24 subjects in each active treatment group, and 24 placebo subjects in each cohort.

Table 4.1.

Cohort	Dosage	Route of Administration	Regimen: Two Doses †		
			No Adjuvant	Al(OH) ₃ ‡	MF59 ‡
1	45 µg	IM (0.5 mL)	24	24	24
	Placebo (saline)	IM (0.5 mL)	24		
2	90 µg	IM (0.5 mL)	24	24	24
	Placebo (saline)	IM (0.5 mL)	24		
3	135 µg	IM (0.5 mL)	24	24	24
	Placebo (saline)	IM (0.5 mL)	24		

For further details please refer to [section 5.1. of the protocol](#).

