8.6 Subgroups

Not applicable.

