9. STUDY SUBJECTS

9.1 Disposition of Subjects and Withdrawals

All subjects who provide informed consent will be accounted for in this study. The frequencies and percentages of subjects in each analysis set, study withdrawals, subgroups, and major protocol deviations will also be presented.

The time the subjects are under observation will be summarized by vaccine and overall using summary statistics (mean, SD, minimum, median, maximum).

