where Y_{ijk} represents the log-transformed (base 10) titer of the k^{th} subject in the dosage group i ($i= 45\mu\text{g}, 90\mu\text{g}$ or $135\mu\text{g}$) and adjuvant group j ($j=$ no adjuvant, aluminum or MF59); μ is the overall mean; α_i is the main effect of dosage i ; β_j is the main effect of adjuvant j , γ is a parameter included to adjust for continuous covariate X_{ijk} representing baseline titer; t_{ijk} are error terms normally distributed with mean zero and variance σ^2 .

The following SAS® code will be used for the ANCOVA model:

```
PROC GLM data = dataset;  
BY antigen visitnum;  
class dosage adjuvant;  
model logtiter_post = dosage adjuvant logtiter_pre;  
LSMEANS dosage adjuvant / stderr tdiff cl pdiff OUT=LSMEANS;  
ESTIMATE "dose 45 vs dose 90" dose 1 -1 0;  
ESTIMATE "dose 90 vs dose 135" dose 0 1 -1;  
ESTIMATE "dose 45 vs dose 135" dose 1 0 -1;  
ESTIMATE "no adj vs alum" adjuvant 1 -1 0;  
ESTIMATE "alum vs MF59" adjuvant 0 1 -1;  
ESTIMATE "no adj vs MF59" adjuvant 1 0 -1;  
RUN;
```

where `logtiter_post` represents the log-transformed antibody value of the immunogenicity variable at a given post baseline timepoint, `dosage` indicates the amount of vaccine content, `adjuvant` the type of adjuvant (i.e none, aluminum hydroxide or

MF59), `logtiter_pre` the log-transformed antibody baseline value of the immunogenicity variable.

Placebo will not be considered in this analysis.

Analysis of interaction:

To test for a possible effect modifier, a dosage by adjuvant interaction will be added to the previous ANCOVA model. With an overall p-value smaller than 0.05, further investigations will be conducted to better understand the degree of the interaction. Additional examinations will include point estimates and 95% CIs for the different levels (e.g. low dosage by no adjuvant, low dosage by alum and so forth) of the factors under study.

4-fold increase:

Proportions of subjects with a ≥ 4 -fold increase in serum anti-RSV NAb titer from baseline will be presented, for each treatment group within each cohort, together with their two-sided 95% Clopper-Pearson CIs (Clopper, 1934). Group differences will not be produced.

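### The dosage contrasts compare sequentially enrolled cohorts without adjusting for sex, and no titre or response result is planned in women

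*SAP*

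**What the plan says.** References are to the last of the three SAP texts in the file.

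- **Sex in the design.** Section 3 says that women and men "will be enrolled in the study in the ratio of 3:1", and explains: "There is a higher ratio of female to male subjects because the RSV F subunit vaccine is ultimately intended for use in pregnant women". The section keeps men because the vaccine may later be tested in the elderly.
- **Cohorts and allocation.** Each dosage is a cohort: "Cohort 1 will be enrolled first, followed by cohort 2, and finally cohort 3". Section 4.1 describes randomisation among the four arms inside a cohort: "Within each cohort, subjects will be randomly allocated (1:1:1:1) to receive vaccine with no adjuvant, vaccine with aluminum hydroxide, vaccine with MF59, or placebo". It refers to protocol section 5.1 for further detail.
- **Models.** Section 8.1 names vaccine group and log baseline titre. Section 11.2 has three ANCOVA models: adjuvant plus baseline within cohort, dosage plus baseline within adjuvant, and the factorial model, coded as "model logtiter_post = dosage adjuvant logtiter_pre". The factorial model leaves out placebo and produces the three pairwise dosage estimates. Section 11.3 reuses these models.
- **Response rates.** The 4-fold-rise proportions are given by treatment group within cohort.
- **Subgroups.** Section 8.6 reads "Not applicable". Section 9.1 nevertheless lists subgroups among the counts to be shown: "The frequencies and percentages of subjects in each analysis set, study withdrawals, subgroups, and major protocol deviations will also be presented".
- **Where sex appears.** Section 10.1 tabulates sex by vaccine group and overall for each cohort, in sets that include the FAS and PPS.

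**The concern.** The plan treats sex as important enough to steer enrolment, then does not use it in the immunogenicity analysis. Two consequences follow.

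First, the comparisons of 45, 90 and 135 µg are comparisons between cohorts filled one after another. Randomisation balances the arms within a cohort but not one cohort against the next. If the sex mix differs between cohorts and the response differs by sex, part of that difference is reported as a dosage effect. Baseline adjustment removes only the part of a sex effect that acts through the pre-vaccination titre. The concurrent placebo groups, which might have helped to expose a cohort difference, are outside the factorial model. The background section says the dosages were chosen to find the dosage-response plateau, so these contrasts carry weight even though section 8.4 makes all tests descriptive.

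Second, the plan gives no Day 57 titre or 4-fold result in women, the sex of the intended users, although the data will be at hand.

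**Working it through.** **Inputs from the SAP.** Three cohorts × four groups × 24 = 288, which reproduces the stated total. At 3:1 that is 288 × 0.75 = 216 women and 72 men. If the ratio held everywhere, each cohort's 72 vaccinated subjects would include 54 women and 18 men, and each group of 24 would include 18 and 6.

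**Assumptions (the SAP gives no values).** Sex effect on the Day 57 titre given baseline, e = 0.05, 0.1 or 0.2 log10, that is a GMT ratio of 10^0.05 = 1.12 to 10^0.2 = 1.58. Residual SD = 0.2, 0.3 or 0.5 log10.

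**Step 1. Chance spread in female share between two dosages.** SD = √(2 × 0.75 × 0.25 / n).
- Factorial model, 72 v 72: √(0.375/72) = 0.072. The 95% limit is 1.96 × 0.072 = 0.141, about 14 points.
- Dosage within one adjuvant, 24 v 24: √(0.375/24) = 0.125. The 95% limit is 1.96 × 0.125 = 0.245, about 25 points.

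**Step 2. Shift in a dosage GMT ratio** = 10^(e × d), where d is the difference in female share.

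| d | e = 0.05 | e = 0.1 | e = 0.2 |
|---|---|---|---|
| 0.141 | 1.016 | 1.033 | 1.067 |
| 0.25 | 1.029 | 1.059 | 1.122 |

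**Step 3. Random error of the same contrast.** 95% CI factor = 10^(1.96 × SD × √(2/n)).

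| SD | 72 v 72 | 24 v 24 |
|---|---|---|
| 0.2 | 1.162 | 1.298 |
| 0.3 | 1.253 | 1.478 |
| 0.5 | 1.457 | 1.918 |

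Every shift in step 2 lies inside the matching interval.

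**Step 4. Chance of a nominal p < 0.05 with no dosage effect (72 v 72).** Put b = e × d / (SD × √(2/72)). The chance is 1 − Φ(1.96 − b) + Φ(−1.96 − b). For e of 0.1 to 0.2 and SD of 0.3 to 0.5, this is 5.3% to 8.7% at d = 0.141 and 6.0% to 17.0% at d = 0.25.

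**Step 5. Precision of a women-only group GMT.** CI factor = 10^(t × SD / √n).

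| SD | all 24 | 18 women |
|---|---|---|
| 0.2 | 1.215 | 1.257 |
| 0.3 | 1.339 | 1.410 |
| 0.5 | 1.626 | 1.773 |

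A women-only summary loses some precision but remains informative.

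**The case against.** The best case for leaving the plan alone runs as follows.

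- **The sex mix may already be controlled.** A reader might infer from section 3 that the ratio binds only over the whole study and that randomisation ignores sex. The document does not show this. Section 4.1 leaves assignment detail to the protocol, where a per-cohort quota or stratification by sex could sit. That part is no finding.
- **No estimate in women is promised.** Section 3 gives a reason for enrolling more women, and no objective in section 2 concerns women separately. With three women in four subjects, the pooled GMT mostly describes women. This stands, so the women's table is an improvement and not the repair of a broken promise.
- **An imbalance would be seen.** Section 10.1 shows sex by group and cohort for the FAS and PPS. This also stands. Seeing an imbalance is not adjusting for it, however, and an adjustment chosen after the results are known is less credible than one fixed beforehand.
- **The effect is small and assumed.** At 72 v 72, a 25-point difference is 0.25/0.072, or about 3.5 chance SDs. This is fair for the factorial model. In the within-adjuvant model, 25 points is about two SDs, though the interval there is wider too.
- **Other factors could also differ between sequential cohorts.** True, and adjusting for sex does not cure that. Sex is singled out because the SAP itself made it a design variable.

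The comparison of adjuvants within a cohort is not affected: allocation there is randomised, so no systematic difference in sex mix arises.

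**Conclusion.** The point holds and is minor. The two section 11.2 models that estimate dosage effects compare non-randomised cohorts and omit the one baseline factor by which the SAP deliberately shapes enrolment. No titre or response result is planned in women.

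For sex effects of 0.05 to 0.2 log10, the shift in a dosage GMT ratio is about 2% to 7% at a 14-point difference in female share and about 3% to 12% at 25 points. The sex effects and residual SDs are assumptions, and exclusions from the PPS would reduce the group sizes used here. The documents do not show that an imbalance will occur or that it would go unnoticed.

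The mention of subgroups in section 9.1 against section 8.6 is a loose end. It promises counts, not a subgroup titre analysis.

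**What to change.** 1. **Section 11.2.** Add sex as a fixed factor to the dosage-within-adjuvant model and to the factorial dosage and adjuvant model, at least as a pre-specified sensitivity analysis. The within-cohort adjuvant model can stay as it is. State how the least squares means weight the two sexes: by default PROC GLM weights them equally, which would describe a 1:1 mix. Observed margins would keep the enrolled mix. The dosage differences themselves do not depend on this choice when sex enters only as a main effect.
2. **Section 8.6.** Replace the present entry with a descriptive summary in women, by group, of the Day 57 NAb GMT and the proportion with a 4-fold or greater rise, each with a 95% CI. This also gives the word in section 9.1 something to refer to.

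The cost is one degree of freedom per model and one table. Sex is already collected. The intervals in women, at about 18 per group, are wider than those for all 24, as step 5 shows.

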13.1.1 Safety Completeness Analysis

Solicited adverse events

The safety completeness analysis on solicited adverse events aims to identify subjects who completed diary cards, irrespective of severity. The analysis will show the number of subjects with *valid data* by solicited adverse event and time point. *Valid data* in the context of the safety completeness analysis are all data entered in the diary card (including implausible values) except “Not done/unknown”.

Four summaries will be produced:

1. The frequencies of subjects who provide diary cards by vaccine group and collection method (i.e., clinical visit, postal mail).
2. For each solicited adverse event, the frequencies of subjects with *valid data* will be presented by vaccine group and time point: 30 min, 6h, days 2, 3, 4, 5, 6 and 7
3. For each type of solicited adverse event (local, systemic) and indicators of solicited adverse events, such as analgesic use, the frequencies of subjects *with valid data* by vaccine group, aggregated over time points: 6h - day 7
4. For each solicited adverse event, the frequencies of subjects *with valid data* by vaccine group, aggregated over time points: 6h - day 7

For the corresponding percentages, the denominator will be the respective numbers of exposed subjects, i.e., subjects who received a vaccination and were still in-study for that time point or time interval, irrespective of whether a diary card was present or not.

All analyses will be based on the ‘as treated’ analysis set.

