13.2 Solicited Local and Systemic Adverse Events

For details please refer to [section 7.1.1 of the protocol](#).

Only solicited local and systemic adverse events reported in the diary card will be analyzed. Implausible measurements will not be taken into consideration in the analysis but listed in the Appendix.

Solicited adverse events will be reported at 30 minutes, at approximately 6 hours post-vaccination on day 1 and then daily until day 7 using structured diaries. The analyses of solicited adverse events will be done separately for 30 minutes and based on three intervals: 6h - day 3, day 4 - 7 and 6h - day 7, each without 30 minutes data. In addition solicited adverse events ongoing after day 7 will be presented as unsolicited AEs.

For erythema, induration and swelling recorded originally as diameters (mm), the following categorization will be used to summarize the data:

Grade 0 (< 25 mm), any (25-50 mm, 51-100 mm, >100 mm)

Body temperature will be broken down by route of measurement according to the recommendations of the Brighton collaboration and will be summarized according to the 3 schemes described below:

- by 0.5 °C increments: <36.0, ≥36.0-<36.5, ≥36.5-<37.0, ≥37.0-<37.5, ≥37.5-<38.0, ≥38.0-<38.5, ≥38.5-<39.0, ≥39.0-<39.5, ≥39.5-<40.0, ≥40.0°C
- by 1.0 °C increments: <36.0, ≥36.0-<37.0, ≥37.0-<38.0, ≥ 38.0-<39.0, ≥39.0-<40, ≥40°C
- <38.0, ≥38.0 °C

Fever, defined as a body temperature of ≥38°C irrespective of route of measurement, will be integrated to the summaries as an indicator of a systemic adverse event.

The analyses will encompass summaries of the data on five levels:

1. Daily reports of subjects with solicited adverse events.
2. Time of first onset of solicited adverse events (excluding 30 min measurement).
3. Solicited adverse events, maximum event severity by event and interval (6h - day 3, day 4 -7, and 6h - day 7, each without 30 min).
4. Duration of solicited adverse events.
5. Solicited adverse events and indicators of solicited adverse events, occurrence of at least one event by category (local, systemic) and interval (6h-Day 3, Day 4-7 and 6h-Day 7, each without 30 min).

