For each of the time points or time intervals presented in the summaries, only subjects with at least one plausible observation (i.e., any non-missing values but excluding “Not done/unknown” and implausible values) for the solicited adverse events in the interval of interest will be considered. Subjects without plausible data (i.e. missing values or reported as “Not done/unknown” and implausible values) will be removed from the denominator to prevent a downward bias (towards zero).

Level 1: Daily reports of solicited adverse event

For each of the time points only subjects with at least one plausible observation (i.e., any non-missing values but excluding “Not done/unknown” and implausible values) for the solicited adverse event in the interval of interest will be considered. Subjects without plausible data (i.e. missing values or reported as “Not done/unknown” and implausible values) will be removed from the denominator in order to prevent a downward bias (towards zero). Data collected will be summarized (frequencies and percentages of subjects) by vaccine group, solicited adverse event, vaccination number and time point.

Level 2: Time of first onset of solicited adverse events

The **time of first onset** is defined, for each subject, for each solicited adverse event, as the time point at which the respective solicited adverse event first occurred. For erythema, induration and swelling the following threshold will be used ≥ 25 mm. The summary will provide the frequencies and percentages of subjects with first onset of each solicited adverse events by vaccine group, by vaccination number, and by each time point.

The tables below show examples of a listing considering four subjects who receive two vaccinations, with post-vaccination data for a given solicited adverse event and a summary table by vaccination group.

Table 13.2-1: Example for Time to First Onset of Solicited Adverse Events

Vaccination	Subject Number	6 Hours	Day 2	Day 3	Day 4	...	Day 7
1	PP D	None	Severe	Moderate	None	...	None
	PP D	Mild	None	None	Moderate	...	Missing
	PP D	Moderate	Mild	None	Severe	...	Mild
	PP D	Mild	Mild	None	None	...	None
2	PP D	None	None	None	None	...	Not done
	PP D	None	Mild	Mild	Missing	...	Missing
	PP D	Severe	None	Mild	Missing	...	None
	PP D	Missing	Missing	Missing	Severe	...	Mild

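### The Visit 6 window lets the dose 2 diary card be collected before its last days are recorded, and the Section 13.2 interval summaries do not say how such cards are handled

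*SAP*

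**What the plan says.** Section 3, Table 3-1, places dose 2 at Visit 5 (Day 29) and Visit 6 at Day 36. The window is -3/+3 days for Visit 6 and -1/+4 days for Visit 2 (Day 8). Three footnotes govern the diary card:

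- Footnote i: entries start 6 hours after each dose and continue "daily thereafter through 7 days after each vaccination".
- Footnote k: "subjects will be reminded that diary cards must be returned at the next clinic visit (Visit 2 or Visit 6").
- Footnote m: "Review of safety data captured on diary cards will be completed at Visit 2 and Visit 6". The cards are then collected and filed.

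Section 13.2 describes solicited events as reported at 30 minutes, "at approximately 6 hours post-vaccination on day 1 and then daily until day 7 using structured diaries". Only diary card data enter the solicited analysis. For each time point or interval the summaries use "only subjects with at least one plausible observation". Level 3 takes the maximum severity seen in the interval. Level 4 counts days with the event and disregards missing days. Level 5 classes a subject as *any* if an event was reported and as *none* in every other case. Section 8.2.1 rules out imputation. Section 13.1.1 tabulates cards by "collection method (i.e., clinical visit, postal mail"). These texts are the same in all three SAP versions in the file.

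**The concern.** The diary period and the collection visit do not fit together after dose 2. A site can follow the schedule exactly and still take the card before the diary period has ended. Because the visit is inside its window, it is not a deviation under Section 6.1. Code 116 in Table 7.8-1 removes only subjects with no solicited data at all.

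The late part of the diary feeds the Day 4–7 and 6h–Day 7 summaries of occurrence, maximum severity and duration. Safety against placebo is a primary objective, with about 24 subjects per group. Any error from a shortened card runs one way, towards fewer, milder or shorter reactions. Section 13.2 removes subjects without data from denominators precisely to avoid a bias towards zero, but the one-observation rule leaves that bias in place when an interval is only partly observed.

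**Working it through.** **Inputs.** From Table 3-1: dose 2 on Day 29; Visit 6 on Day 36, -3/+3; Visit 2 on Day 8, -1/+4; reminder calls after dose 2 on Days 31 and 33, -1/+1. From Section 13.2: diary Day 1 is the vaccination day and the last analysed day is Day 7.

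**Reproducing the plan's figures.** Visit 6 is 36 − 29 = 7 days after dose 2, as Table 3-1 states. The day counts in the Table 13.2-3 example (2, 4, 11, 0, 2, 4) all reproduce, including a card with Days 4–7 missing that counts as 2 days. The vaccination 2 denominators in Table 13.2-2 (3, 3, 3, 2, 2) reproduce when missing days leave the denominator.

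**Earliest collection.**

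- Visit 6: 36 − 3 = Day 33; 33 − 29 = 4 days after dose 2; 4 + 1 = diary Day 5.
- Visit 2: 8 − 1 = Day 7; 7 − 1 = 6 days after dose 1; 6 + 1 = diary Day 7.
- Second reminder call after dose 2: 33 + 1 = Day 34 at the latest, so it can come after the card has been handed in.

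| Visit 6 on Day | Days after dose 2 | Diary day of visit | Diary days not yet reached | Same-day entry at risk |
|---|---|---|---|---|
| 33 | 4 | 5 | 6, 7 | 5 |
| 34 | 5 | 6 | 7 | 6 |
| 35 | 6 | 7 | none | 7 |
| 36–39 | 7–10 | 8–11 | none | none |

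Footnote i counts days after vaccination, which run one behind the diary labels of Section 13.2. On that count a Day 33 card lacks days 5, 6 and 7, and the earliest Visit 2 lacks day 7 after dose 1. The diary labels are used here because the analysis uses them. The table takes the Visit 6 window as counted from dose 2. Table 3-1 does not say so, and Visit 5 may itself be up to 14 days late.

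**What Section 13.2 does with a Day 33 card.** Take a subject with no event through Day 5, Days 6–7 missing and a true first event on Day 6.

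- Daily tables, Days 6 and 7: not in the denominator, so not counted as *none*.
- Level 5, Day 4–7 and 6h–Day 7: in the denominator through the observed days, classed *none*.
- Level 3: the maximum is taken over the observed days only.
- Level 4: missing days add 0. A reaction present on every day from Day 1 to Day 7 is counted as 5 days (4 if the Day 5 entry is also missing), not 7.

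**Size.** The SAP gives neither the share of early cards nor the share of late first onsets, so both are assumed. Understatement of the 6h–Day 7 *any* rate = share of cards taken early × share of subjects with first onset after collection.

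- Low: 0.10 × 0.02 = 0.2 percentage points; 24 × 0.002 = 0.05 subjects per group.
- Middle: 0.25 × 0.05 = 1.25 points; 0.3 subjects.
- High: 0.50 × 0.10 = 5.0 points; 1.2 subjects.

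**The case against.** The strongest case against has five parts.

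- **The loss is possible, not certain.** It arises only at early visits, and Section 13.1.1 mentions return by post. This stands as a limit on size. It does not remove the conflict, because footnote k makes return at Visit 6 mandatory.
- **Missing days are mostly handled.** A reader might infer that Days 5–7 after dose 2 are lost and counted as *none* throughout. The SAP does not support that. In the diary labels the days lost are 6 and 7, with Day 5 at risk. Daily tables drop missing days from the denominator, and a subject with an earlier event in the interval remains *any*. Misclassification is confined to subjects whose first event in the interval follows collection.
- **Missing days would be visible.** Section 13.1.1 counts valid data at each time point from 6 hours to Day 7. That is true, but the table is not expressly split by dose and does not correct the interval results. The 14- and 21-day interviews cannot refill tables built from diary data only.
- **All arms share the window.** Nothing suggests differential loss by arm. However, equal proportional undercounting still shrinks the absolute vaccine–placebo difference. A reader might also infer a distorted dose 2 versus dose 1 comparison. The SAP tabulates by vaccination number but plans no such comparison.
- **The frequency is unknown.** If visits were spread evenly over the seven permitted days, 2/7 (29%) of cards would miss Day 7, or 3/7 (43%) if the visit came before that day's entry. Nothing in the SAP supports an even spread, and these figures count early cards, not misclassified subjects.

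**Conclusion.** The point holds in limited form. Footnotes k and m, with the Visit 6 window, conflict with footnote i, and an in-window visit can end the dose 2 diary at Day 5, or at Day 4 if that day's entry is not yet made. For such cards the Level 5 interval results can record *none* wrongly, and Levels 3 and 4 can be understated; the daily tables are not affected in this way. The date arithmetic is certain, provided the window is counted from dose 2. The effect is not known. The range of 0.2 to 5.0 percentage points (0.05 to 1.2 subjects per group of 24) rests wholly on assumed inputs and is small at its lower end. The conflict should still be settled, because the error can only make dose 2 look better tolerated and the correction is cheap.

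**What to change.** **Collection.** Reconcile footnotes k and m and the Visit 6 window with footnote i. The card may be reviewed at Visit 6 but is collected only after the last required entry, by post (already listed in Section 13.1.1) or at the next clinic visit. State which entry is the last, since footnote i and Section 13.2 count days differently, and what the Visit 6 window is counted from. Card return is a site procedure, so the protocol and site instructions must carry the same wording.

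**Analysis.** In Section 13.2, report by vaccine group and dose the number of subjects with an incomplete Day 4–7 or 6h–Day 7 interval. Repeat the interval summaries in subjects with every day of the interval observed, applying completeness alike to those with and without events. This assumes that coming early is unrelated to reactions.

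Do not drop only the incomplete non-events. As an illustration, take 24 subjects, 6 with events, all recorded before collection (25%), and 7 early cards of which 2 have events. Dropping only the 5 early non-events gives 6/(24 − 5) = 6/19 = 31.6%, too high by 6.6 points. Dropping all 7 early cards gives (6 − 2)/(24 − 7) = 4/17 = 23.5%.

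**Cost.** Some cards arrive later, and one completeness flag and one extra table are needed. The analysis part can be added to the SAP even if collection practice can no longer change.
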